8.3.7 REPORTING EVENTS TO PARTICIPANTS

Not Applicable

8.3.8 EVENTS OF SPECIAL INTEREST

Not Applicable

8.3.9 REPORTING OF PREGNANCY

Not Applicable

8.4 UNANTICIPATED PROBLEMS

8.4.1 DEFINITION OF UNANTICIPATED PROBLEMS (UP)

The Office for Human Research Protections (OHRP) considers unanticipated problems involving risks to participants or others to include, in general, any incident, experience, or outcome that meets **all** of the following criteria:

- Unexpected in terms of nature, severity, or frequency given (a) the research procedures that are described in the protocol-related documents, such as the Institutional Review Board (IRB)-approved research protocol and informed consent document; and (b) the characteristics of the participant population being studied;
- Related or possibly related to participation in the research (“possibly related” means there is a reasonable possibility that the incident, experience, or outcome may have been caused by the procedures involved in the research); and
- Suggests that the research places participants or others at a greater risk of harm (including physical, psychological, economic, or social harm) than was previously known or recognized.

8.4.2 UNANTICIPATED PROBLEM REPORTING

The Primary Investigator will report unanticipated problems (UPs) to the reviewing Institutional Review Board (IRB). The UP report will include the following information:

- Protocol identifying information: protocol title and number, PI’s name, and the IRB project number;
- A detailed description of the event, incident, experience, or outcome;
- An explanation of the basis for determining that the event, incident, experience, or outcome represents an UP;
- A description of any changes to the protocol or other corrective actions that have been taken or are proposed in response to the UP.

To satisfy the requirement for prompt reporting, UPs will be reported using the following timeline:

- UPs that are serious adverse events (SAEs) will be reported to the IRB and to the study sponsor within 7 days of the investigator becoming aware of the event.
- Any other UP will be reported to the IRB and to the study sponsor within 14 days of the investigator becoming aware of the problem.
- All UPs should be reported to appropriate institutional officials (as required by an institution’s written reporting procedures), the supporting agency head (or designee), and the Office for Human Research Protections (OHRP) within 7 days of the IRB’s receipt of the report of the problem from the investigator.

8.4.3 REPORTING UNANTICIPATED PROBLEMS TO PARTICIPANTS

Not Applicable

9 STATISTICAL CONSIDERATIONS

9.1 STATISTICAL HYPOTHESES

Primary Endpoint: The WebApp is safe, usable, acceptable, and participants will be willing to use the WebApp.

Secondary Endpoint: The explore preliminary differences between the intervention and control groups in regards to experiences of sexual violence victimization and perpetration, rape myth acceptance, and sexual relationship power.

9.2 SAMPLE SIZE DETERMINATION

Formal sample size calculations were not performed because this is a pilot feasibility study. The number of subjects was chosen based on feasibility and is considered sufficient to meet the study objectives.

9.3 POPULATIONS FOR ANALYSES

All data collected through the pilot study process will be utilized for the analyses related to feasibility, usability, and acceptability. The data collected from the semi-structured interview subjects will be utilized to analyze the safety of the application and the willingness of participants to use the application.

9.4 STATISTICAL ANALYSES

9.4.1 GENERAL APPROACH

The survey data will be analyzed using the Statistical Package for the Social Sciences (SPSS); all p-values will be set at $<.05$. Descriptive statistics will be assessed first. The baseline, 3-month post, and 6-month post-intervention tests will be examined for measures of central tendency, measures of dispersion, and frequency distribution on outcomes. Analysis of variance (ANOVA) will be utilized to determine if the scores on the baseline and follow-up tests differ significantly among the two arms. Usability and acceptability scores will be assessed among those in the intervention group.

We are not powered to assess outcome measures (sexual violence experiences/behaviors, rape myth acceptance, or sexual relationship power); however, we will look at the direction of effects for our outcome measures to allow for power calculations for a future R-Level submission. The results of this project will establish the safety and usability of this adapted web-based application for future scale-up.

For the semi-structured interviews, all audiotapes will be transcribed verbatim. Data analyses will be conducted using an iterative process and the constant comparative method of analysis (Glaser, 1992). Member checking will contribute to credibility through validation of the research findings by participants. A codebook will be developed after repeated high-level reading of the transcripts by the study team. Data will be coded and grouped into categories to facilitate abstraction and concept analysis.

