Quad) at the University of Michigan will be randomized to receive either: (1) the control arm (n=150) which will receive usual care only (all incoming students receive three programs about healthy relationships and sexual violence including Haven, Relationship Remix, and Change it Up) or (2) the usual care (n=150) described above and the web-based intervention (MKit). We will use cluster-randomization by residence hall (to minimize contamination associated with individual-level randomization of students living in the same residence hall). Following the informed consent process, students in both conditions will complete a baseline survey of 85 questions. Baseline measures will include: 1) demographic data, 2) 20 items from the Sexual Experiences Survey (SES) will measure past experiences with sexual violence (Koss et al., 2007), 3) investigator developed questions on knowledge about sexual violence, 4) 22 items from the modified Illinois Rape Myth Acceptance Scale to measure attitudes endorsing rape myths (McMahon & Farmer, 2011), and 4) 6 items from the Sexual and Relationship Power Scale (SRPS) will measure the multidimensional nature of power in relationships (Pulerwitz & Barker, 2000). All of these are measures have been validated and used extensively in the United States to measure knowledge and attitudes related to gender based violence. Following the survey, students in the Intervention group will be given the opportunity to interact with the application at their own pace, choosing which content to view in the order they prefer.

The Control group will only receive the usual care delivered to all incoming University of Michigan students, which includes Haven (an online course about sexual violence), Relationship Remix (an interactive program about healthy relationships and sexual violence delivered by peers), and Change it Up (a theater based performance on bystander intervention). The Intervention group will receive the usual care described above as well as access to the adapted web-based application. They will be encouraged to interact with the web-based application throughout the study. Data will be collected on the content viewed by the participants, as well as the amount of time they spend within each content area, and the order in which they view the content.

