At 3 and 6 months, we will repeat all baseline measures in both groups. Participants in the Intervention group will also be asked to complete the 10-item System Usability Scale (Brooke, 1996) and an investigator creates 5-item acceptability scale.

Post-intervention semi-structured interviews will be conducted with 25 participants including 15 participants from the intervention group and 10 participants from the control group to assess perceived safety, reaction to content, desirability, willingness to continue using the content, and willingness to recommend the content to others. Prior to commencing the interviews, we will ask each participant to complete a paper demographic survey.

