5.5 STRATEGIES FOR RECRUITMENT AND RETENTION

Students from the target sample, first-year University of Michigan college students, will be recruited for the study. Two residence halls (West Quad and South Quad) at the University of Michigan will be randomized to receive either: (1) the control arm (n=150) which will receive usual care only (all incoming students receive three programs about healthy relationships and sexual violence including Haven, Relationship Remix, and Change it Up) or (2) the usual care (n=150) described above and the web-based intervention (MKit). We will use cluster-randomization by residence hall (to minimize contamination associated with individual-level randomization of students living in the same residence hall). At the end of the Relationship Remix program, a brief announcement will be made about the opportunity to participate in a research study about healthy relationships and palm cards will be distributed (see recruitment materials). We will recruit specifically from Relationship Remix to ensure that all experimental and control subjects receive the same primary prevention programming currently in place on campus. Interested students will receive a palm card with a link to either the MKit web-based application (Intervention) with an access code to sign-up for the website, or a link to the baseline consent and Qualtrics survey (Control) without access to the web-based application. At the end of the study, students from each condition will be invited to participate in an in-person semi-structured interview. Students will receive the invitation to participate in the semi-structured interview on the final page of their 6-month follow-up survey. Students who opt to share their email address with the study team at that time will be contacted to set-up an in-person interview based on user status for the intervention (consistent user of MKit, frequent user of MKit, minimal user of MKit) and a diverse group based on gender, race/ethnicity, and age for the control group. Semi-structured interviews will be conducted with participants from both the Control group (n=10) and the Intervention group (n=15).

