6.3 MEASURES TO MINIMIZE BIAS: RANDOMIZATION AND BLINDING

Study subjects will be randomized into one of two groups: 1) Intervention (WebApp and current prevention programming on campus) or 2) Control (current prevention programming on campus only), with 150 students in each group. We will use cluster-randomization by residence hall (to minimize contamination associated with individual-level randomization of students living in the same residence hall).

This study will not involve blinding.

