9.4.2 ANALYSIS OF THE PRIMARY ENDPOINT

The safety of the WebApp and the willingness of participants to use the WebApp will be assessed through post-intervention semi-structured interviews, conducted with 25 participants including 15 participants from the intervention group and 10 participants from the control group. The usability for the WebApp will be assessed at two time points (3-months and 6-months) using the 10-item System Usability Scale (Brooke, 1996). The acceptability of the WebApp will be assessed at two time points (3-months and 6-months) using an investigator created 5-item acceptability scale. Usability and acceptability scores will be assessed among those in the intervention group.

For the semi-structured interviews, all audiotapes will be transcribed verbatim. Data analyses will be conducted using an iterative process and the constant comparative method of analysis (Glaser, 1992). Member checking will contribute to credibility through validation of the research findings by participants. A codebook will be developed after repeated high-level reading of the transcripts by the study team. Data will be coded and grouped into categories to facilitate abstraction and concept analysis. An audit trail will be established to allow others to follow the decisions made by the research team (Sandelowski & Barroso, 2003). The results of the semi-structured interviews will be used to: 1) update the content of the WebApp, as needed; 2) assess the safety of the WebApp; 3) assess the usability and willingness to use the WebApp; and 4) assess the acceptability of the WebApp.

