9.4.3 ANALYSIS OF THE SECONDARY ENDPOINT

Preliminary analyses of the survey data (sexual violence victimization and perpetration, rape myth acceptance, and sexual relationship power) will be analyzed using the Statistical Package for the Social Sciences (SPSS); all p-values will be set at $<.05$. Descriptive statistics will be assessed first. The baseline, 3-month post, and 6-month post-intervention tests will be examined for measures of central tendency, measures of dispersion, and frequency distribution on outcomes. Analysis of variance (ANOVA) will be utilized to determine if the scores on the baseline and follow-up tests differ significantly among the two arms. Usability and acceptability scores will be assessed among those in the intervention group.

We are not powered to assess outcome measures (sexual violence experiences/behaviors, rape myth acceptance, relationship power); however, we will look at the direction of effects for our outcome measures to allow for power calculations for future scale-up.

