9.4.7 SUB-GROUP ANALYSES

Primary and secondary endpoints will be analyzed based on gender, race/ethnicity, student group involvement, sexual orientation, and relationship status.

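### With one residence hall per arm, the between-arm ANOVA at p<.05 on the secondary outcomes has no valid error term and cannot separate the app effect from the hall effect

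*Combined protocol and SAP*

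**What the plan says.** Section 5.5 sets the allocation: "Two residence halls (West Quad and South Quad) at the University of Michigan will be randomized to receive either" control or intervention, with 150 students in each. Section 4.1 gives the reason for allocating by hall: "We will use cluster-randomization by residence hall (to minimize contamination associated with individual-level randomization of students living in the same residence hall". Section 6.3 opens with "Study subjects will be randomized into one of two groups", which on its own could be read as individual randomisation, but its next sentence confirms that the unit is the hall.

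The analysis is in 9.4.1: "Analysis of variance (ANOVA) will be utilized to determine if the scores on the baseline and follow-up tests differ significantly among the two arms", with the p-value threshold at .05. Section 9.4.3 applies the same test to the secondary outcomes: "Preliminary analyses of the survey data (sexual violence victimization and perpetration, rape myth acceptance, and sexual relationship power) will be analyzed using" the same software, threshold and ANOVA. Neither section mentions a hall term, an ICC, a design effect, a cluster adjustment or any limit on attributing a difference to the app.

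Three other statements matter here. Section 4.1 provides repeated measurement: "At 3 and 6 months, we will repeat all baseline measures in both groups". Section 9.4.7 adds subgroups: "Primary and secondary endpoints will be analyzed based on gender, race/ethnicity, student group involvement, sexual orientation, and relationship status". For two of the primary endpoints, 9.4.2 says: "Usability and acceptability scores will be assessed among those in the intervention group".

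**The concern.** The unit allocated is the hall, but the unit analysed is the student. With a single hall in each arm, anything that distinguishes West Quad from South Quad (who lives there, local programming, events during the year) is carried entirely by the arm comparison. The plan's own reason for allocating by hall is that students who live together influence one another, so it has no ground for treating hall-mates as independent.

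A significant difference on victimization or perpetration, rape myth acceptance or relationship power could therefore come from the halls and not the app, and a real app effect could be hidden in the same way. Section 9.4.1 intends to use the direction of these effects for the power calculations of a later study, and 4.2 treats gathering data for those calculations as central to the pilot. A direction that mixes hall and app would be carried into the next design.

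**Working it through.** The plan has no figure to reproduce, since 9.2 states that no sample size calculation was done.

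**Inputs from the documents.** Two halls, one per arm (4.1, 5.5); n = 150 students per hall (4.1, 5.5, 6.3); threshold .05 (9.4.1, 9.4.3); measures at baseline, 3 and 6 months in both arms (4.1).

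**Assumed, because the documents give no values.** ICC from 0.001 to 0.05; correlation of a student's scores between waves r = 0.5; correlation of the hall effect between waves c = 1, 0.8 or 0.5; 75 students per hall in a subgroup; a true app effect of 0.2 SD for the direction check.

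**Step 1: degrees of freedom (no assumption needed).** Halls within arm: 2 halls − 2 arms = 0. A hall-level t test, a mixed model or a cluster-robust standard error has no between-hall variance to estimate within an arm. The only residual available is between students within a hall.

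**Step 2: ANOVA at a single wave.** Design effect DEFF = 1 + (n − 1) × ICC. True type I error of the nominal 5% test = 2 × [1 − Φ(1.96/√DEFF)]. For example, at ICC 0.01, DEFF = 1 + 149 × 0.01 = 2.49, √2.49 = 1.58, and the error is 2 × [1 − Φ(1.96/1.58)] = 21%.

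| ICC | DEFF | Type I error, n = 150 | Type I error, n = 75 (subgroup) |
|---|---|---|---|
| 0.001 | 1.149 | 7% | 6% |
| 0.005 | 1.745 | 14% | 9% |
| 0.01 | 2.49 | 21% | 14% |
| 0.02 | 3.98 | 33% | 21% |
| 0.05 | 8.45 | 50% | 37% |

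Simulating the one-way F test (40,000 replicates, two halls of 150, no app effect) gave 0.067, 0.140, 0.217, 0.331 and 0.513, and 0.051 at ICC 0.

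**Step 3: ANOVA on change from baseline.** The plan does not say which form of ANOVA it means, and the repeated measures make this form possible. A hall difference that is constant over time cancels. In units of the total variance at one wave:

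- hall variance of change = 2 × ICC × (1 − c)
- student variance of change = 2 × (1 − ICC) × (1 − r)
- inflation = 1 + 150 × hall variance / student variance, used in place of DEFF in Step 2.

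For example, at ICC 0.01 and c = 0.8, inflation = 1 + 150 × 0.004/0.99 = 1.606, and the type I error is 12%.

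| ICC | c = 1 | c = 0.8 | c = 0.5 |
|---|---|---|---|
| 0.001 | 5% | 6% | 7% |
| 0.005 | 5% | 9% | 14% |
| 0.01 | 5% | 12% | 22% |
| 0.02 | 5% | 19% | 33% |
| 0.05 | 5% | 34% | 51% |

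The 5% level holds only in the c = 1 column, where the halls would have moved in parallel without the app. With one hall per arm the data cannot show which column applies.

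**Step 4: direction of effect.** With a true effect of 0.2 SD, P(correct sign at a single wave) = Φ(0.2/√[(2/150) × DEFF]). This is 96% at ICC 0, then 95%, 91%, 86%, 81% and 72% across the five ICCs. For change from baseline with c = 0.8, the same calculation with standard error √{2 × [hall variance + student variance/150]} gives 95%, 94%, 92%, 88% and 81%.

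**Step 5: what more students would do.** The chance difference between two halls has SD √(2 × ICC), which is 0.14 outcome SDs at ICC 0.01 and 0.32 at ICC 0.05. The standard error from a student-level analysis is √(2/150) = 0.115. Recruiting more students per hall shrinks the second figure and leaves the first unchanged.

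**The case against.** The strongest reply is that little hangs on this test. The study is labelled a quasi-experimental before-and-after pilot, efficacy is not primary (8.1), the secondary outcomes are declared not powered, and no success criterion depends on the between-arm p-value. All of that is true and limits the severity. It does not withdraw the significance test. Low power means that a real effect may be missed; the fault here is a false-positive rate that is not 5%.

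A second reply is that the size is uncertain and partly overstated. A before-and-after design points at least as naturally to change scores, for which inflation is smaller when hall effects are stable. Loss to follow-up also lowers it: with 100 students per hall, the single-wave rates are 6%, 11%, 16%, 26% and 42%. This stands as a caution about the numbers. Only the zero degrees of freedom and the aliasing of arm with hall are free of assumptions.

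A third reply is that, if the two halls are taken as fixed, student-level variance does answer whether these two groups of students differ. That is correct, but the plan compares arms to learn about the app, and attribution to the app is what fails. Recruiting everyone from Relationship Remix (5.5) and comparing baseline characteristics (9.4.5) make gross imbalance less likely or more visible. Neither rules out halls that diverge during the year.

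Finally, 9.4.7 specifies no between-arm subgroup test, so the point reaches subgroups only if such tests are done. Section 4.2 gives central importance to obtaining data for power calculations in general, not to direction of effect, and much of that purpose survives.

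**Conclusion.** The concern holds. With one hall per arm, the ANOVA in 9.4.1 and 9.4.3 has no valid error term for an effect of the app, and no reanalysis of two halls can supply one. That conclusion needs no assumption.

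Its size does. A single-wave test is valid only if the ICC is exactly 0, and the false-positive rate is 7% to 50% over ICC 0.001 to 0.05 with the planned 150 students per hall. A change-from-baseline test ranges from 5% (parallel halls) to 51% (ICC 0.05, c = 0.5, r = 0.5). These ranges are illustrative.

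The fault covers the between-arm comparisons of victimization and perpetration, rape myth acceptance and relationship power, and any between-arm subgroup tests on them. The primary endpoints are not affected: usability and acceptability are assessed within the intervention group, and safety and willingness come from interviews. It should be fixed, but it does not threaten the pilot's main purpose.

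**What to change.** In 9.4.1 and 9.4.3, and for the secondary outcomes in 9.4.7:

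- Remove the between-arm ANOVA significance test and the p<.05 rule.
- Report summaries for each hall at each wave, and change within each hall.
- Give the difference between halls, preferably in change from baseline, as descriptive only, with this sentence: *One hall per arm: hall and intervention effects cannot be separated.*
- Optionally, show how the standard error of a single-wave difference would grow: multipliers √DEFF of 1.07, 1.32, 1.58, 1.99 and 2.91 for ICC 0.001, 0.005, 0.01, 0.02 and 0.05, labelled as assumed values.

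In the secondary objective (section 3) and 9.4.3, state that the pilot supplies standard deviations, event rates, baseline-to-follow-up correlations and retention for later power calculations. State also that it supplies neither an unconfounded app effect size nor an ICC, should the later study be cluster-randomised.

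The primary endpoint analyses need no change. The cost is wording only, with no effect on recruitment or data collection. The pilot gives up reporting significant between-arm differences, which it could not validly report.

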9.4.2 ANALYSIS OF THE PRIMARY ENDPOINT

The safety of the WebApp and the willingness of participants to use the WebApp will be assessed through post-intervention semi-structured interviews, conducted with 25 participants including 15 participants from the intervention group and 10 participants from the control group. The usability for the WebApp will be assessed at two time points (3-months and 6-months) using the 10-item System Usability Scale (Brooke, 1996). The acceptability of the WebApp will be assessed at two time points (3-months and 6-months) using an investigator created 5-item acceptability scale. Usability and acceptability scores will be assessed among those in the intervention group.

For the semi-structured interviews, all audiotapes will be transcribed verbatim. Data analyses will be conducted using an iterative process and the constant comparative method of analysis (Glaser, 1992). Member checking will contribute to credibility through validation of the research findings by participants. A codebook will be developed after repeated high-level reading of the transcripts by the study team. Data will be coded and grouped into categories to facilitate abstraction and concept analysis. An audit trail will be established to allow others to follow the decisions made by the research team (Sandelowski & Barroso, 2003). The results of the semi-structured interviews will be used to: 1) update the content of the WebApp, as needed; 2) assess the safety of the WebApp; 3) assess the usability and willingness to use the WebApp; and 4) assess the acceptability of the WebApp.

